₹ Pfizer C	CLINICAL AND MEDICAL CONTROLLED DOCUMENT (CMCD) REQUIRED FORM/TEMPLATE			
Identifier	Version	Title	Effective Date	
CT24-WI-GL02-	2.0	SUMMARY OF CHANGES IN	01-Jun-2022	
RF07		AMENDED NON-INTERVENTIONAL		
		STUDY PROTOCOL		

Protocol #: C4221028

OCEANMIST - Comparative effectiveness of different targeted therapies for BRAF-mutated unresectable/metastatic melanoma in the United States

SUMMARY OF CHANGES IN AMENDED NON-INTERVENTIONAL STUDY PROTOCOL

This amended protocol describes a revised approach for assessment of comparative effectiveness of encorafenib plus binimetinib relative to other targeted therapies for BRAF-mutated unresectable/metastatic melanoma. Analyses conducted based on the originally submitted protocol for study C4221028 were limited to descriptive and unadjusted analyses of real-world data from Flatiron Health, as the sample size of the identified encorafenib plus binimetinib study cohort was judged to be too small for conduct of adjusted comparative effectiveness analyses. Based on the findings of a recently completed study (*Protocol #C4221035: Overall survival (OS) in patients with metastatic BRAFV600-mutant melanoma treated with encorafenib plus binimetinib in the COLUMBUS trial versus in real-world practice data)*, which showed consistent OS outcomes between the COLUMBUS trial Flatiron Health after accounting for differences in patient profiles, in this amended protocol, to enrich the sample size for the encorafenib plus binimetinib combination cohort, data will be pooled across Flatiron and COLUMBUS, and compared versus real-world data for other targeted therapies as described further below.

Key elements of the revised approach are summarized below:

- 1. Pooling of data for encorafenib + binimetinib patients across the phase 3 COLUMBUS trial and the Flatiron Health real-world database: The pooling of data for encorafenib + binimetinib patients across these two sources is justified by the results of study C4221035, which showed, that after harmonizing key patient selection criteria, adjusting for differences in baseline characteristics, and imputing missing data on baseline characteristics, OS for metastatic BRAFV600-mutant melanoma patients was similar across the COLUMBUS trial and real-world practice data from the Flatiron Health database (HR = 1.03, 95% CI: 0.53, 1.54; p=0.90). Given this empirical consistency in OS outcomes, pooling patients across these settings can be justified and allows for a larger sample size for assessment of comparative effectiveness of encorafenib + binimetinib versus other targeted therapies.
- 2. Application of key patient selection criteria consistent with the COLUMBUS trial for all treatment groups: To ensure included patient populations are comparable across settings, key patient selection criteria applied from the COLUMBUS trial will also be applied to all treatment groups drawn from the Flatiron real-world database. These include the following: age ≥18 years at initiation of targeted therapy, metastatic BRAF V600E/K mutated melanoma without central nervous system metastases, untreated or with prior first-line immunotherapy, and ECOG performance status of 0 or 1.
- Imputation of missing data on baseline characteristics: To allow for more
 comprehensive adjustment for confounding due to differences in baseline characteristics
 between treatment groups, multiple imputation will be conducted to account for missing
 data in baseline characteristics.

The approach outlined here largely follows the approach described in *Protocol #C4221035*, with minor updates to the selection criteria, adjustment factors and statistical methods following discussions with a clinical expert in melanoma and further review of the clinical trial and real-world data.

Classification of Change as Substantial and Non-Substantial and Rationale

This is a Substantial Protocol Amendment for the reasons described above.

NON-INTERVENTIONAL (NI) STUDY PROTOCOL

Study information

Title	OCEANMIST - Comparative effectiveness of different targeted therapies for BRAF-mutated unresectable/metastatic melanoma in the United States	
Protocol number	C4221028	
Protocol version identifier	2.0	
Date	19 JUL 2023	
Active substance	Encorafenib plus Binimetinib	
Medicinal product	Braftovi ® plus Mektovi®	
Research question and objectives	The study objective is to describe and compare OS in patients with metastatic BRAFV600-mutant melanoma treated with encorafenib plus binimetinib (ENCO+BINI) versus other targeted therapies.	
Author(s)	PPD PharmD, MS PPD PPD ScD PPD Analysis Group, Inc. PPD	
	PPD PhD PPD , Analysis Group, Inc. PPD , ScD	
	PPD , Analysis Group, Inc. PPD PhD PPD , Analysis Group, Inc. PPD , Analysis Group, Inc.	

This document contains confidential information belonging to Pfizer. Except as otherwise agreed to in writing, by accepting or reviewing this document, you agree to hold this information in confidence and not copy or disclose it to others (except where required by applicable law) or use it for unauthorized purposes. In the event of any actual or suspected breach of this obligation, Pfizer must be promptly notified.

2. LIST OF ABBREVIATIONS

Abbreviation	Definition	
1L	First-line	
AE	Adverse event	
AJCC	American Joint Committee on Cancer	
BMI	Body mass index	
BRAF	v-Raf murine sarcoma viral oncogene homolog B protein	
CI	Confidence interval	
CTD	Clinical trial data	
DAB+TRAM	Dabrafenib + Trametinib	
ECOG	European Cooperative Oncology Group	
EHR	Electronic health record	
ENCO+BINI	Encorafenib + Binimetinib	
FDA	Food and Drug Administration	
GPP	Good Pharmacoepidemiology Practices	
GRACE	Good Research for Comparative Effectiveness	
HIPAA	Health Insurance Portability and Accountability Act	
HR	Hazard ratio	
ICD-9	International Classification of Diseases 9th Revision	
ICD-10	International Classification of Diseases 10th Revision	
IEC	Independent Ethics Committee	
Ю	Immunotherapy	
IRB	Institutional Review Board	
ISPE	International Society for Pharmacoepidemiology	
ISPOR	International Society for Pharmacoeconomics and Outcomes Research	
KM	Kaplan-Meier	
LDH	Lactate dehydrogenase	
LOT	Line of therapy	

MEK	Mitogen-activated protein kinase (MAPK) kinase
MICE	Multiple imputation by chained equations
NDI	National Death Index
NI	Non-interventional
OS	Overall survival
PFS	Progression free survival
RECIST	Response Evaluation Criteria in Solid Tumours
RWD	Real-world data
SMR	Society of Melanoma Research
TT	Targeted therapy
US	United States
VEM+COBI	Vemurafenib + Cobimetinib

4. AMENDMENTS AND UPDATES

Significant updates have been made to the data source and analytical approach compared to the original OCEANMIST protocol submission. Below, we provide a high-level overview of the key differences with additional details described in Sections 5-8 and Section 12 below.

Data Source Updates

• In this study, data for encorafenib plus binimetinib patients will be pooled from the phase 3 COLUMBUS trial and the Flatiron Health real-world database to maximize sample size. In contrast, the original study design, only used encorafenib plus binimetinib data from Flatiron Health. This pooling is justified based on the empirical consistency in OS outcomes across COLUMBUS and Flatiron Health after harmonizing key patient selection criteria, adjusting for differences in baseline characteristics, and imputing missing data on baseline characteristics (HR = 1.03, 95% CI: 0.53, 1.54; p=0.90), described in study C4221035.

Analytical Approach Updates

- To ensure identification of patient populations in Flatiron that are comparable to patients in the COLUMBUS trial, key patient selection criteria related to age, ECOG performance score, history of brain metastasis and prior use of immunotherapy and targeted therapies from the COLUMBUS trial will be applied to all treatment groups in Flatiron Health.
- To ensure that representation of each targeted therapy from the real-world data was as comprehensive as possible and that patients were followed from treatment initiation consistent with the COLUMBUS trial, patients included in each treatment cohort will be required to have index dates (i.e., treatment initiation dates) that were on or after the dates of FDA approval of that targeted therapy in metastatic melanoma (specifically, 09 January 2014 for DAB+TRAM, 10 November 2015 for VEM+COBI and 27 June 2018 for ENCO+BINI). This is in contrast to the original approach, which defined the follow-up period for all cohorts as beginning from 20 November 2015. This could have led to the exclusion of some patients initiating DAB+TRAM before approval, and could potentially inadvertently include off-label usage of ENCO+BINI.
- For the real-world cohorts, patient baseline characteristics will be obtained from visits ≤3 months prior to the index date, with data from visits closest in time to the index date being used as available. In contrast, in the original protocol, to maximize availability of baseline characteristics, the 'baseline' period was allowed to include visits up to 6 months prior to treatment initiation. The decision to use a stricter definition of baseline here was based on clinical input that certain baseline characteristics of interest (e.g., ECOG PS) are best assessed closest to the index date, despite potential for increased missingness. To address missingness, imputation of baseline characteristics was conducted as described below.

- Key clinical characteristics like ECOG and LDH were missing at baseline for 40-60% of
 patients in the original study cohort, which would have hampered ability to adjust for
 potential confounding due to these factors. To address missingness, we will impute data
 using multiple imputation by chained equations prior to conducting adjusted analyses.
 Imputation models will be based on baseline characteristics that would be considered in
 adjusted models for OS.
- Inverse probability of treatment weighting without any imputation was proposed in the
 original study design to account for baseline differences. Instead, we will use
 multivariable Cox proportional hazards models fit to each of the imputed dataset and
 combined results across all imputations. This approach is preferred as it allows us to
 assess how included covariates are associated with OS in our final models, in addition to
 estimating differences between the treatments of interest.
- Comparisons of OS and PFS were stratified by first-line and second-line of therapy in the
 original study design. Analyses conducted in this revised protocol will not be stratified by
 line of therapy to allow for a larger sample size to compare OS and PFS across targeted
 therapy treatment cohorts. A line of therapy variable will be included in Cox proportional
 hazard models, which can facilitate future analyses of comparative effectiveness by line
 of therapy if required.

5. MILESTONES

Milestone	Planned date
Amendment to study protocol	19 May 2023
Completion of statistical analyses	7 June 2023
Abstract submission to Society for Melanoma Research (SMR) 2023 Congress	21 June 2023
Final study report	21 July 2023

6. RATIONALE AND BACKGROUND

Melanoma, caused when malignant cancer cells form in melanocytes, is the fifth most common cancer in the United States (US) and the deadliest form of skin cancer. Incidence of melanoma has been increasing over recent decades, with the overall incidence rate of 229.1 cases per million person based on recent estimates. Based on American Cancer Society estimates, there were an estimated 99,780 new cases of melanoma and ~7,650 deaths from melanoma in the US in 2022. 1-3

Approximately 9% of melanoma patients are diagnosed with regional spread to lymph nodes and 4% are diagnosed with metastatic disease. Compared to patients with localized melanoma, patients with metastatic melanoma have poorer prognosis and worse outcomes, which can be further worsened by the presence of v-Raf murine sarcoma viral oncogene homolog B protein (BRAF) mutations. The BRAF protein plays an important role in normal cell growth, proliferation, differentiation, and survival. The presence of BRAF V600 mutations, found in ~40–60% of melanoma cases, can lead to sustained mitogen-activated protein kinase (MAPK) kinase (MEK) pathway signaling, resulting in tumor growth and progression.

Recommended treatment options for metastatic melanoma include immunotherapy (IO), which attempts to stimulate host responses to effectuate tumor destruction, and targeted therapies (TT), which inhibit molecular pathways to prevent tumor growth and maintenance. The discovery of targeted therapy as a treatment for melanoma has emerged as a milestone development in oncological research. In 2018, the US Food and Drug Administration (FDA) approved the use of encorafenib (BRAFTOVI®) in combination with binimetinib (MEKTOVI®) for the treatment of patients with unresectable or metastatic melanoma with a BRAF V600E or V600K mutation (as detected by an FDA-approved test) based on the pivotal phase 3 COLUMBUS trial. This accompanied existing BRAF-/MEK-inhibitor therapies including dabrafenib plus trametinib (FDA approval 10 November 2015).

There is increasing interest in evaluating comparative effectiveness of BRAF-/MEK-inhibitor therapies. In a recent study, we showed that overall survival (OS) for metastatic BRAFV600-mutant melanoma patients was similar across the COLUMBUS trial and real-world practice data from the Flatiron Health database (Hazard Ratio [HR] = 0.94, 95% Confidence Interval [CI]: 0.43, 1.45) after harmonizing key patient selection criteria, adjusting for differences in baseline characteristics, and imputing missing data on baseline characteristics. Given this empirical consistency in OS outcomes, pooling patients across these settings can be justified and allows for a larger sample size for assessment of comparative effectiveness of encorafenib + binimetinib versus other targeted therapies. To that end, this study will expand on this prior work and compare OS between patients receiving encorafenib + binimetinib in the pooled Phase 3 COLUMBUS trial and the Flatiron Health Electronic Health Records (EHR) database versus patients receiving other targeted therapies. Baseline profiles of patients will also be compared to characterize differences in patients receiving different therapies and adjustments will be made for

differences across treatment groups in baseline factors associated with OS. Missingness for key baseline characteristics will be addressed using a validated multiple imputation approach.¹²

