8.7.4. Adjusted comparison of OS between treatment groups

Finally, an adjusted comparison of OS across treatment groups (i.e., ENCO+BINI [pooled across COLUMBUS and Flatiron EHR], DAB+TRAM and VEM+COBI) will be conducted. Hazard ratios will be estimated based on a multivariable Cox proportional hazard model, adjusting for key baseline characteristics known or expected to be related to OS in metastatic melanoma (e.g., age, sex, race, BMI, ECOG, LDH, time from initial melanoma diagnosis to metastatic disease, time from metastatic diagnosis to treatment initiation, treatment experience in the therapeutic setting, prior IO/chemotherapy in the adjuvant setting, prior surgery in the adjuvant setting). Specific adjustment factors listed here may be revised based on expert clinical input.

The adjusted analyses will be conducted in each of the datasets with imputed baseline characteristic values in turn. Log-hazard ratios for OS comparing treatment with ENCO+BINI relative to DAB+TRAM and VEM+COBI each imputed dataset will be obtained, and summary HRs obtained by pooling results across all imputed datasets will be generated using Rubin's rules. ¹⁶

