There is increasing interest in evaluating comparative effectiveness of BRAF-/MEKinhibitor therapies. In a recent study, we showed that overall survival (OS) for metastatic BRAFV600-mutant melanoma patients was similar across the COLUMBUS trial and real-world practice data from the Flatiron Health database (Hazard Ratio $\lceil HR \rceil = 1.03$, 95% Confidence Interval [CI]: 0.53, 1.54; p=0.90) after harmonizing key patient selection criteria, adjusting for differences in baseline characteristics, and imputing missing data on baseline characteristics. Given this empirical consistency in OS outcomes, pooling patients across these settings can be justified and allows for a larger sample size for assessment of comparative effectiveness of encorafenib + binimetinib versus other targeted therapies. To that end, this study will expand on this prior work and compare OS between patients receiving encorafenib + binimetinib in the pooled Phase 3 COLUMBUS trial and the Flatiron Health Electronic Health Records (EHR) database versus patients receiving other targeted therapies. Baseline profiles of patients will also be compared to characterize differences in patients receiving different therapies and adjustments will be made for differences across treatment groups in baseline factors associated with OS. Missingness for key baseline characteristics will be addressed using a validated multiple imputation approach. 12

This non-interventional study is not designated as a Post-Authorization Safety Study (PASS) and it is not a commitment or requirement to any regulatory authority.

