2.1 STUDY DESIGN

This is a retrospective cohort study comparing OS outcomes between patients with BRAFV600-mutant metastatic melanoma initiating encorafenib plus binimetinib (ENCO+BINI) versus dabrafenib plus trametinib (DAB+TRAM) or vemurafenib plus cobimetinib (VEM+COBI). Comparisons will be adjusted for differences in baseline characteristics across treatment groups, and account for missing data on adjustment factors. PFS will also be investigated as an exploratory endpoint, subject to comparability of PFS outcome assessment between clinical trial and real-world settings.

Study population

The study population will consist of patients with BRAFV600-mutant metastatic melanoma initiating treatment with ENCO+BINI, DAB+TRAM or VEM+COBI. Data for ENCO+BINI will be pooled across COLUMBUS and Flatiron data, while data for DAB+TRAM and VEM+COBI will be from Flatiron data. The number of patients eligible for the study will be determined in accordance with the sample selection conducted per the inclusion and exclusion criteria described in Section 4.

Data source

COLUMBUS trial

COLUMBUS was a two-part, multicenter, randomized, open-label, Phase 3 clinical trial. Part 1 of the trial investigated the effectiveness and safety of three treatment regimens in patients with locally advanced unresectable or metastatic BRAFV600-mutant metastatic melanoma who were treatment naïve or whose cancer had progressed after 1L IO. In Part 1 of the trial, patients were randomized to one of three treatment arms: 1) 450mg once daily encorafenib and 45mg twice daily binimetinib (n=192), 2) 960mg twice daily vemurafenib (n=191) and 3) 300mg once daily encorafenib (n=194). Randomization was stratified by AJCC disease stage (IIIB, IIIC, IVM1a, IVM1b, or IVM1c), ECOG performance status (0, 1), and BRAFV600 mutation profile (V600E, V600K). Progression-free survival was the primary endpoint in the trial, while OS was one of the secondary endpoints. Patients were enrolled in Part 1 of the trial between 30 December 2013 through 10 April 2015.

The ENCO+BINI arm of Part 1 of the trial will be used in this study (database lock date: 15 September 2020) and combined with the ENCO+BINI cohort from Flatiron EHR identified below. Part 2 of the trial compared encorafenib 300mg once daily plus binimetinib 45mg twice daily versus encorafenib 300mg once daily alone and will not be considered.

Flatiron Health EHR

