The adjusted analyses will be conducted in each of the datasets with imputed baseline characteristic values in turn. Log-hazard ratios for OS comparing treatment with ENCO+BINI relative to DAB+TRAM and VEM+COBI each imputed dataset will be obtained, and summary HRs obtained by pooling results across all imputed datasets will be generated using Rubin's rules. 16

Exploratory analyses of PFS

Analyses assessing PFS will also be explored. PFS will be defined as described in Section 8.3. PFS will be summarized for all treatment groups.

Suitability of comparative analyses of PFS between treatment groups will be determined following additional data exploration to characterize number and frequency of assessments of PFS available in these settings, and discussion of comparability of the assessment of disease progression in RWD vs CTD. If analyses of PFS are deemed suitable based on these evaluations, unadjusted and adjusted comparisons of PFS will be conducted using the methods described for OS above.

Sensitivity analyses

Two sets of sensitivity analyses may be pursued. First, Cox regression analyses for OS and PFS may be repeated with adjustment for additional covariates based on clinical input. Second, given differences in timing of approvals of each of the targeted therapies of interest, and changes in the treatment landscape over the time frame, analyses exploring sensitivity of the results to time frames of treatment initiation may also be explored based on clinical input.

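### COLUMBUS patients enter only the ENCO+BINI arm, no analysis separating the data sources is committed to, and the hazard ratio justifying the pooling conflicts between Protocol 6 and SAP 2 and is too imprecise to show similarity

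*Protocol*

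**What the plan says.** **Who is in which arm.** SAP 2.1 pools ENCO+BINI across COLUMBUS and Flatiron, "while data for DAB+TRAM and VEM+COBI will be from Flatiron data". Protocol 8.4 puts the COLUMBUS ENCO+BINI arm at 192 randomised patients. The Flatiron ENCO+BINI count is not given; SAP 1 says that cohort was judged too small for adjusted comparison.

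**The model.** Protocol 8.7.4 compares "ENCO+BINI [pooled across COLUMBUS and Flatiron EHR], DAB+TRAM and VEM+COBI" in a multivariable Cox model. The listed covariates there, in SAP 7.1 and in Appendix Table 3 of both documents include no data source, region or calendar year. Table 1 in Protocol 8.3 lists year and region as baseline characteristics but does not mark them as potential confounders. The list is open: "Specific adjustment factors listed here may be revised based on expert clinical input".

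**The justification.** Pooling rests on study C4221035. Protocol 6 reports an HR of 0.94, "95% Confidence Interval [CI]: 0.43, 1.45". SAP 2 reports 1.03, "95% Confidence Interval [CI]: 0.53, 1.54; p=0.90". Both sections conclude that "Given this empirical consistency in OS outcomes, pooling patients across these settings can be justified".

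**What might test it.** SAP 4.2 plans no subgroups. SAP 7.1 names two optional sensitivity analyses: "Cox regression analyses for OS and PFS may be repeated with adjustment for additional covariates based on clinical input", and "analyses exploring sensitivity of the results to time frames of treatment initiation may also be explored based on clinical input". Neither mentions data source, and the second gives no dates. Protocol 8.9 accepts that geography and care setting may affect outcomes and that number and sites of metastases cannot be adjusted for.

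**The concern.** Every COLUMBUS patient received ENCO+BINI and every comparator patient is from Flatiron. If trial patients live longer or shorter than comparable practice patients, for reasons that the covariates miss, the pooled model has nowhere to put that difference except the treatment coefficient. It could then be reported as one drug combination being better or worse than another.

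The only protection is the claim that the two sources have similar OS. That claim is quoted with two different estimates in current text, without a stated reference group, and with intervals that do not establish similarity. This plan also changes C4221035's selection criteria, adjustment factors and methods in minor ways (Protocol, summary of changes), so the earlier result does not carry over exactly.

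The year and region rows of Appendix Table 1 would show roughly how much of the ENCO+BINI arm is COLUMBUS. They would not show what that does to the HR.

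**Working it through.** **1. Reproducing the stated p-value.** Inputs: HR 1.03, limits 0.53 and 1.54 (SAP 2). On the HR scale, SE = (1.54 - 0.53)/3.92 = 0.258, z = 0.03/0.258 = 0.116 and p = 0.907, or 0.891 to 0.923 allowing for rounding of the inputs. The stated 0.90 is reproduced. It means that no difference was detected.

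**2. Are the two HRs one result inverted?** 1/0.94 = 1.06, with limits 1/1.45 = 0.69 and 1/0.43 = 2.33. 1/1.03 = 0.97, with limits 1/1.54 = 0.65 and 1/0.53 = 1.89. Neither matches the other. Only Protocol 6 and SAP 2 are relied on here, not the amendment summaries.

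**3. Width.** The half-widths are 0.51/0.51 (0.94 version) and 0.50/0.51 (1.03 version), so both intervals are symmetric on the HR scale, which is unusual for a Cox model. If they are Wald limits on that scale, the log-scale SEs are (1.02/3.92)/0.94 = 0.277 and (1.01/3.92)/1.03 = 0.250. HR × exp(±1.96 × SE) then gives about 0.55 to 1.62 and 0.63 to 1.68. The documents state no similarity margin. Taking 0.80-1.25 and 0.67-1.50 as assumed margins, none of the four intervals fits inside either.

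**4. How far a source difference moves the treatment HR.** Assumptions: no true drug difference; source HR read as COLUMBUS versus Flatiron; treatment HR as ENCO+BINI versus comparator (Appendix Table 3 prints the inverse); 192 COLUMBUS patients (upper bound); 30 to 100 Flatiron ENCO+BINI patients (assumed). COLUMBUS share = 192/222 = 0.865 to 192/292 = 0.658. Approximate apparent HR = (source HR)^share.

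| Source HR | Origin | Apparent HR, 30 Flatiron patients | Apparent HR, 100 Flatiron patients |
|---|---|---|---|
| 0.94 | Protocol 6 estimate | 0.95 | 0.96 |
| 1.03 | SAP 2 estimate | 1.03 | 1.02 |
| 0.80 | assumed | 0.82 | 0.86 |
| 1.25 | assumed | 1.21 | 1.16 |
| 0.43 / 1.45 | Protocol 6 limits | 0.48 / 1.38 | 0.57 / 1.28 |
| 0.53 / 1.54 | SAP 2 limits | 0.58 / 1.45 | 0.66 / 1.33 |
| 0.55 / 1.62 | 0.94 version, log scale | 0.60 / 1.52 | 0.67 / 1.37 |
| 0.63 / 1.68 | 1.03 version, log scale | 0.67 / 1.57 | 0.74 / 1.41 |

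The approximation weights by patients. COLUMBUS has longer follow-up, so its share of deaths may be higher and the shift somewhat closer to the source HR.

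**5. Calendar time.** COLUMBUS enrolled from 30 December 2013 to 10 April 2015 (Protocol 8.4). DAB+TRAM indexing starts after 9 January 2014 and overlaps it. VEM+COBI indexing starts after 10 November 2015, 214 days after COLUMBUS enrolment closed. Flatiron ENCO+BINI starts after 27 June 2018, 1,174 days after it closed. Within ENCO+BINI, a window of treatment initiation therefore determines which source is analysed.

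**The case against.** **The conflicting HRs are editorial, since both are near 1.** As point estimates they lead to almost the same small shift, and that stands. The conflict still needs correcting, because this is the one result on which the pooling rests, and the intervals matter more than the estimates.

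**The direction can be inferred.** The title of C4221035 suggests COLUMBUS versus real world. That is a hint; no reference group is stated beside either HR.

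**The limitations are disclosed and sensitivity analyses exist.** Protocol 8.9 is candid, and the time-frame analysis could separate the sources indirectly. It is optional and undated, so it does not replace a committed contrast.

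**A source split brings back the contrast that pooling was meant to avoid.** This is largely true. With no comparator patients in COLUMBUS, a source effect can be estimated only from ENCO+BINI patients, and the Flatiron-only contrast loses most of the precision gained by pooling. That is a reason to keep the pooled model and show the split beside it.

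**The study is not powered for formal testing (SAP 3.2).** Agreed. The point concerns how the primary OS estimate is read.

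A reader might also infer that deaths are counted differently in the two sources. The documents do not support that: Protocol 8.9 cites validation of the Flatiron mortality endpoint against the National Death Index.

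**Conclusion.** The point holds and should be fixed. Arm and source are confounded by design, no committed analysis separates them, and the current texts give two incompatible HRs for the result that is meant to make this harmless. Neither shows similarity.

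The size is uncertain. At the documents' own point estimates the shift is small (0.95-0.96 or 1.02-1.03). A moderate assumed source effect of 0.80 or 1.25 would give 0.82-0.86 or 1.16-1.21. The wider figures in the working show what the intervals leave open, not what is expected. All rest on the assumed Flatiron count, on 192 COLUMBUS patients and on the source HR being COLUMBUS versus Flatiron.

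Three stronger readings are not supported. A reader might infer that the pooled HR is biased, or biased towards ENCO+BINI; the documents establish neither. A reader might take 0.43 and 1.54 together as one range; they belong to conflicting versions of one result, and no printed interval spans both. A reader might conclude that the two sources differ in OS; a wide interval does not show that either, and the C4221035 report is not available here.

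**What to change.** 1. **Reconcile the HR.** Check Protocol 6 and SAP 2 against the C4221035 report, give one value with its reference group, and say how the interval was computed. Replace the claim of empirical consistency with: *No difference in OS was detected; the interval does not exclude a substantial difference in either direction.*

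2. **Add one supplementary model** in Protocol 8.7.4 and SAP 7.1/7.2, leaving the pooled model unchanged. Use the same adjusted Cox model with a four-level exposure: ENCO+BINI-Flatiron, ENCO+BINI-COLUMBUS, DAB+TRAM, VEM+COBI. In a separate panel of Appendix Table 3, report with CIs each comparator versus each ENCO+BINI source, and COLUMBUS versus Flatiron within ENCO+BINI. Keep the direction of the existing rows. Label the panel supplementary, with no pass/fail rule, and add the note: *The pooled HR includes any residual difference between trial and practice.* Protocol 5 planned completion of analyses for 7 June 2023, before the protocol date of 19 July 2023; if they are already complete, label the panel post hoc.

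3. **If the time-frame analysis is run,** state its dates and which ENCO+BINI source each window leaves.

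**Cost.** One extra model on existing data, one table panel and some wording. The Flatiron-only contrast will be imprecise. With assumed cohorts of 30-100 Flatiron ENCO+BINI, 240 DAB+TRAM and 60 VEM+COBI patients, simulated SEs of the log HR run from 0.144 to 0.444. Raising the largest by an assumed 20% for adjustment and imputation gives 0.533. The 95% limits then lie a factor of exp(1.96 × 0.144) = 1.33 to exp(1.96 × 0.533) = 2.84 either side, roughly 1.3 to 2.8. It therefore cannot replace the pooled HR.
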